Table 4	TEAEs in $\geq 2\%$ of subjects in either SB206 treated group or Vehicle group (NI-MC302)	28
Table 5	BOTE Inflammation Score	50
Table 6	Local Skin Reaction Scale	53
Table 7	Study Drug	55
Table 8	Assessment of Causality	61
Table 9	Grading System for Patch Test Reactions (at each time point)	77
Table 10	Challenge Reaction Interpretation (based on the last reading (at least 48 hours after patch removal)	77

LIST OF FIGURES

Figure 1	Study Timeline Diagram	20
Figure 2	NI-MC301: Percentage of Subjects with Complete Clearance	28
Figure 3	NI-MC302: Percentage of Subjects with Complete Clearance	29
Figure 4	Structure of Berdazimer Sodium (active ingredient in SB206)	56

LIST OF APPENDICES

Appendix 1	Procedure for Suspected Sensitization	76
------------	---	----

LIST OF ABBREVIATIONS

Abbreviation	Definition
AD	Atopic Dermatitis
AE	Adverse Event
BID	Twice Daily
BOTE	Beginning-of-the-end
BSA	Body Surface Area
CFR	Code of Federal Regulations
CM	Concomitant Medication
CRO	Clinical Research Organization
CSR	Clinical Study Report
DSMB	Data and Safety Monitoring Board
ECG	Electrocardiogram
e-consent	Electronic Consent
eCRF	Electronic Case Report Form
ET	Early Termination
FDA	Food and Drug Administration
GCP	Good Clinical Practice
GEE	Generalized Estimating Equation
hMAP3	Hydrolyzed N-Methylaminopropyl-trimethoxysilane
IB	Investigator's Brochure
ICF	Informed Consent Form
ICH	International Conference on Harmonisation
IEC	Independent Ethics Committee
IP	Investigational Product
IRB	Institutional Review Board
ITT	Intent-to-Treat
IUD	Intrauterine Device
IUS	Intrauterine Hormone Releasing System
IWRS	Interactive Web Response System

LLOQ	Lower Limit of Quantitation
LSR	Local skin reaction (post exposure to study drug)
MC	Molluscum Contagiosum
MedDRA	Medical Dictionary of Regulatory Affairs
NO	Nitric Oxide
NOVAN	Novan, Inc.
OTC	Over the counter
PK	Pharmacokinetic
PP	Per-Protocol Population
QD	Once daily
SAE	Serious Adverse Event
SAF	Safety Population
SAP	Statistical Analysis Plan
SD	Standard Deviation
SOA	Schedule of Assessments
SOC	System Organ Class
SOP	Standard Operating Procedure
TEAE	Treatment Emergent Adverse Event
UPT	Urine Pregnancy Test

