
¹ Screening and Baseline may occur on the same day. If this occurs, lesion count and review of inclusion/exclusion criteria will only occur once.
 
² All visit dates are in reference to Baseline (e.g. Week 2 occurs 14 days after Baseline Visit). The Week 4 visit may be performed remotely or in clinic. Baseline, Week 2, Week 8, Week 12, and 24 visits will be performed in clinic. Day 2, Week 16, and Week 20 will be performed via phone. If a subject terminates early, an in-clinic visit is preferred, but a remote visit may be performed with sponsor approval.
 
³ Lesion counts will be performed twice during the Baseline visit; the first assessment will be performed by the investigator in person, and the second assessment will be performed by the investigator through image evaluation.
 
⁵ The physical exam will include a directed examination of the skin (presence or absence of individual features of erythema, flaking/scaling, crusting, swelling, vesiculation/pustulation, and erosion/ulceration).
 
⁶ Females who have reached 9 years of age, unless they are post-menopausal (at least 12 months of continuous amenorrhea without an alternative medical cause), or surgically sterilized (documented hysterectomy, documented bilateral salpingectomy, or documented bilateral oophorectomy). Tubal ligation does not meet the definition of surgically sterile.
 
⁷ UPT will be performed at Screening if the visit takes place in the clinic.
 
⁸ BOTE Inflammation Score will be assessed pre-dose at Baseline. The Baseline LSR assessment should be done at least 30 minutes after study drug is applied on Day 1. After Baseline, BOTE Inflammation score and LSRs can be evaluated at any time pre- or post-dose during the visit, regardless of whether lesions are present and whether study drug is applied.
 
⁹ Study drug application will occur in clinic at Baseline, Week 2, Week 4, Week 8, and Week 12. On days when a remote visit will occur, subjects/caregivers will not apply the study drug until the study visit so that the mixing/application of study drug can be observed by site staff during the remote visit.
 
¹⁰ At Screening, subjects should be asked if any household members currently have MC. In addition to recording AE and CM changes, subjects should be asked if there are any new occurrences of MC in household members of subjects at each visit, except Day 2.
 
¹¹ Follow up interviews will be performed with selected consented subjects that complete Week 12. Consent can be obtained starting at Baseline, and the follow up interview will be performed with the subject/caregiver at a later date.
 
NOTE: The Week 4 visit can be performed in clinic or remote. Baseline, Week 2, Week 8, Week 12, and Week 24 should be performed in clinic wherever possible. Day 2, Week 16, Week 20 should be performed as telephone contacts. Unscheduled visits are permitted as needed for medical reasons. In-clinic unscheduled visits should be reserved for evaluation of adverse events, lesion clearance, and study drug dispensation as needed. Remote unscheduled visits may be utilized as well as/if applicable.
			

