6.6 Order of Assessments

At the Baseline visit on Day 1, the physical examination and BOTE Inflammation Score should be done prior to randomization to study treatment. For WOCBP (see definition in Section 9.4), the UPT must be done prior to randomization. The initial Local Skin Reaction (LSR) assessment should be done at least 30 minutes after study drug is applied on Day 1. The BOTE and LSR assessments should be completed at each scheduled visit even if the subject is not going to be dosed or if the MC lesions have cleared. It may be most convenient to perform lesion counting, mapping, and scarring assessments immediately following the BOTE and LSR assessments. In order to ensure consistent counting of MC lesions, the same assessor should complete the lesion counts at all visits, but at a minimum, at Baseline and Week 12.

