7.2.3 Local Skin Reaction Assessment

The investigator (or designated evaluator) will assess localized skin reactions (LSRs) at Baseline (at least 30 minutes post-dose), and at any time during the visit at Weeks 2, 4, 8 and 12. The individual components of LSRs are scored separately on a scale of 0-4, with higher numbers indicating more severe reactions. The individual components include erythema, flaking/scaling, crusting, swelling, vesiculation/pustulation, and erosion/ulceration.

Compared to BOTE, LSRs are generally more diffuse, associated with significant itch or tenderness, may necessitate discontinuation of study treatment, and may need treatment for symptomatic relief (e.g. a topical corticosteroid or topical anesthetic). For very severe LSR, systemic corticosteroids may be considered.

Investigators will assess the treatment area at each scheduled visit and use their medical judgement to differentiate between BOTE and LSRs. When LSRs are clinically significant in the opinion of the investigator (i.e. they interfere with the subject's normal daily activities), s/he should report the condition as an AE(s) (e.g. application site erythema, application site edema).

Clinically significant LSRs that are reported as adverse events and/or subject reported intolerability (i.e. itching, pain) may result in an investigator directed temporary treatment hold

(drug holiday), and topical corticosteroids may be used to treat LSRs for up to 2 weeks. The subject may re-initiate study drug treatment prior to the next scheduled visit. Upon re-initiation (challenge) of study drug treatment, if a subject develops worsening LSRs (more severe than the first LSRs), allergic contact dermatitis may be suspected. In the event of suspected allergic contact dermatitis, photographs may be taken of the affected area(s) and transmitted to the CRO medical monitor for review and confirmation of allergic contact dermatitis prior to initiating patch testing. Consent must be in place for patch testing to occur. The investigator should also discuss the necessity of patch testing with the subject/caregiver. The investigator will then discontinue the subject from study drug treatment and treat the area(s) with corticosteroids for up to 2 weeks. If the subject provides consent/assent, the investigator will consult the CRO medical monitor to implement the process for patch testing. See Section 7.2.5 for information on patch testing.

Table 6 Local Skin Reaction Scale

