## 6. GENERAL ANALYSIS CONSIDERATIONS

The statistical analyses will be reported using summary tables, listings, and figures (TLFs). The International Council for Harmonisation (ICH) numbering convention will be used for all TLFs. Unless otherwise noted, all statistical testing will be two-sided and will be performed at the 0.05 significance level. Tests will be declared statistically significant if the calculated  $P$ -value is  $\leq 0.05$ .

Continuous variable summaries will include the number of subjects ( $n$ ) with non-missing values, mean, standard deviation (SD), median, minimum, and maximum. Other statistics such as quartiles, confidence intervals (CIs), and number of missing values may be added as appropriate.

Categorical variable summaries will include the frequency and percentage of subjects who are in the category or each possible value. In general, the denominator for the percentage calculation will be based upon the total number of subjects in the study population within each treatment group, unless otherwise specified. The denominator for by-visit displays will be the number of subjects in the relevant study population with non-missing data at each visit.

All summary tables will be presented by treatment group. Baseline summaries will also include an overall summary column.

Individual subject data obtained from the eCRFs and any derived data will generally be presented by subject in data listings. Additionally, a listing of the subjects requiring a narrative because they experience one of the following events: serious adverse event, death, discontinued the study due to an AE, hypertrophic or keloid scarring, unresolved scars, or LSR suggestive of allergic contact dermatitis will be presented.

A separate report for the results from the study exit interview will be created.

The analyses described in this plan are considered a priori, in that they have been defined prior to breaking the blind.

Any analyses performed subsequent to breaking the blind will be considered post hoc and exploratory. Post hoc analyses will be labeled as such on the output and identified in the clinical study report.

All analyses and tabulations will be performed using SAS® software Version 9.4 or higher. Tables, listings, and figures will be presented in RTF format.

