#### 13.1 Adverse Events

Adverse event summaries restricted to treatment-emergent AEs (TEAEs) will include those AEs that occurred any time on or after the first in-clinical application of study drug through the last application of study drug and those existing AEs that worsened during this same period. If it cannot be determined whether the AE is treatment emergent due to a partial onset date, then it will be counted as such; see Appendix A for the imputation of missing dates algorithm. Post treatment AEs will include those AEs that occurred after the last application of study drug. Verbatim terms in the eCRFs will be mapped to preferred terms and system organ classes using the MedDRA Version 23.0 or later.

Each AE summary will be displayed by treatment group. Summaries that are displayed by system organ classes and preferred terms will be ordered by descending order of incidence in SB206 treatment group of system organ class and preferred term within each system organ class. Summaries of the following types will be presented:

- Overall summary of TEAEs and post treatment AEs that contain an overview of each item below.

- Subject incidence of TEAEs with total number of unique TEAEs and post treatment AEs with total number of unique post treatment AEs by MedDRA system organ class and preferred term.
- Subject incidence of TEAEs and post treatment AEs by MedDRA system organ class, preferred term, and maximum severity. At each level of subject summarization, a subject is classified according to the maximum severity if the subject reported 1 or more events. Adverse events with missing severity will be considered severe for this summary.
- Subject incidence of TEAEs by MedDRA system organ class, preferred term, and closest relationship to study drug (Related/Not Related). Related AEs are those reported as “Definite,” “Probable,” or “Possible,” and unrelated AEs are those reported as “Unlikely” or “Unrelated.” At each level of subject summarization, a subject is classified according to the closest relationship if the subject reported 1 or more events. Adverse events with a missing relationship will be considered related for this summary.
- Subject incidence of serious TEAEs with total number of unique serious TEAEs and post treatment serious AEs with total number of unique post treatment serious AEs by MedDRA system organ class and preferred term.

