### **13.2 Local Skin Reaction**

The LSR composite score will be calculated by summing up all the numerical responses (0-4) to each individual parameter for a composite score that ranges between 0 and 24. The observed and change from Baseline values of the LSR composite score will be summarized descriptively at each visit. This analysis will be repeated based on the dichotomized baseline BOTE score described in Section 12.

A table summarizing each LSR parameter (erythema, flaking/scaling, crusting, swelling, vesiculation/pustulation, and erosion/ulceration) score at each scheduled post-baseline assessment will be presented. This analysis will be repeated based on the dichotomized baseline BOTE score described in Section 12.

Additionally, a shift table comparing the baseline score for each LSR parameter to each scheduled postbaseline assessment will be presented for the Safety Population.

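### The by-visit LSR tables pool subjects on and off study drug, so Week 12 (and to a lesser extent Week 8) probably understates on-drug reactions on SB206; a supplementary split by treatment status would show it

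*Protocol*

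**What the plan says.** Protocol 1.2 (Table 1 footnote) allows post-baseline LSR scoring at any time in the visit, "regardless of whether lesions are present and whether study drug is applied". Protocol 6.6 asks for the assessment at each scheduled visit "even if the subject is not going to be dosed or if the MC lesions have cleared". Protocol 7.2.3 fixes the post-baseline occasions: "and at any time during the visit at Weeks 2, 4, 8 and 12".

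Subjects who go off drug stay under assessment. Under Protocol 4.1 the investigator may stop treatment on clearance while visits and non-drug procedures continue. Under Protocol 6.8.1 a subject stopped for an AE remains in the study.

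On the analysis side, SAP 13.2 states: "The observed and change from Baseline values of the LSR composite score will be summarized descriptively at each visit". Component scores and shifts are handled the same way, and the only further split is by baseline BOTE. SAP 6 adds: "The denominator for by-visit displays will be the number of subjects in the relevant study population with non-missing data at each visit". For AEs, by contrast, SAP 13.1 counts as treatment-emergent those occurring "on or after the first in-clinical application of study drug through the last application of study drug", and tabulates post-treatment AEs separately.

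**The concern.** Change from Baseline in LSR score is a named safety endpoint. A by-visit LSR row mixes two kinds of subject: those whose skin is still exposed, and those whose drug was held or stopped. If the second group scores lower and is larger on SB206, the SB206 row falls over time for a reason unrelated to tolerance. The arm difference narrows with it. A reader of Tables 14.3.6.1.1 to 14.3.6.1.5 could not tell skin that has adapted from drug that has been stopped.

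The documents make lower off-drug scores plausible:
- Protocol 2.1.4.2 attributes all SB206 drug discontinuations in the earlier phase 3 studies to application site reactions, so this route removes reactors.
- Protocol 7.2.3 allows corticosteroids for such reactions.
- Protocol 9.2.2 lists abating on discontinuation among the signs of a related event.

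**Working it through.** Neither document states an LSR level or an expected off-drug share, so the plan has no figure of its own to reproduce on this point.

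**Inputs from the protocol**
- Drug stopped for a TEAE (Table 2): SB206 7/235 = 3.0% and 17/237 = 7.2%; vehicle 1/116 = 0.9% and 1/117 = 0.9%. These match the printed percentages. Pooled: 24/472 = 5.1% vs 2/233 = 0.9%.
- Complete clearance at Week 8 (2.1.4.3): 15.3% vs 10.3% in NI-MC301 and 13.9% vs 5.9% in NI-MC302. Weighted by the Table 2 group sizes: SB206 (0.153×235 + 0.139×237)/472 = 14.6%; vehicle (0.103×116 + 0.059×117)/233 = 8.1%.

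**Assumptions, not in the documents**
- s, the fraction of cleared subjects who actually stop: 0, 0.5 or 1, because stopping on clearance is optional.
- On-drug rate of any LSR: 40% on SB206, 15% on vehicle.
- Off-drug rate: 0 first, then 15%, 40% and 60%, the same in both arms.

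**Formulas**
- Off-drug share at Week 12: q = AE-stop share + s × Week 8 clearance share.
- Pooled rate = (1 − q) × on-drug rate + q × off-drug rate.

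**Result with no LSR off drug** (on-drug difference 25 points; rounded after calculation)

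| s | q, SB206 vs vehicle | Subjects of 425 per arm | Pooled rates | Difference (points) |
|---|---|---|---|---|
| 0 | 5.1% vs 0.9% | 22 vs 4 | 38.0% vs 14.9% | 23.1 |
| 0.5 | 12.4% vs 4.9% | 53 vs 21 | 35.0% vs 14.3% | 20.8 |
| 1 | 19.7% vs 8.9% | 84 vs 38 | 32.1% vs 13.7% | 18.5 |

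For s = 1, SB206 is 0.40 × (1 − 0.197) = 0.321 and vehicle is 0.15 × (1 − 0.089) = 0.137.

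**Sensitivity to the off-drug rate** (difference in points at s = 0, 0.5, 1)
- 15% off drug: 23.7, 21.9, 20.1.
- 40% off drug: 24.8, 23.8, 22.8. SB206's own rate is not understated.
- 60% off drug: 25.6, 25.3, 24.9. SB206's own rate is overstated, at 41.0%, 42.5% and 43.9%.

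Over on-drug rates of 30% vs 10% to 60% vs 20%, with off-drug rates of 0-15%, the relative loss in the arm difference runs from about 5% to 26%.

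The SAP plans no by-visit rate of any LSR; that rate is only an illustration. A mean composite score is the same mixture, so with off-drug scores of 0 the SB206 mean would fall by the fraction q, about 5-20%.

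**Which visits.** Protocol 8.2 has treatment run to Week 4 at a minimum, so stops for clearance can affect only Weeks 8 and 12. The Week 8 clearance rates bear on Week 12. The text gives no Week 4 clearance rate, so Week 8 cannot be sized in the same way.

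**The case against.** The strongest case on the other side has five parts.

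1. **Pooling is legitimate.** An all-treated summary answers a proper question, and scoring subjects off drug is sound data collection. This stands: the gap lies in SAP 13.2, not in the schedule footnote.

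2. **Other outputs show the reactions.** SAP 13.3 counts subjects with at least one post-baseline LSR component score of 1 or more, and a later 0 cannot erase an earlier reaction. Clinically significant LSRs are also recorded as AEs. This stands, so a reader who infers that SB206's reactions are hidden goes too far. But SAP 13.3 gives no time course or grade distribution, and it also counts scores taken off drug.

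3. **The off-drug shares lean high.** Table 2 runs through Week 24. The two stopping routes may overlap. Some AE stoppers leave the study and so drop out of the denominator. Cleared subjects may restart for new or recurring lesions. Temporary holds, which are not counted, work the other way.

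4. **One rule can push Week 12 upward.** Protocol 7.2.5 has Week 12/ET assessments done when drug is stopped for suspected allergic contact dermatitis. SAP 7 treats such a record as Week 12 if no Study Exit form has the same date. A score taken during the reaction could then sit in the Week 12 row. This stands, and it makes the pooled row harder to read.

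5. **An on-drug table is itself selected.** Subjects who could not tolerate the drug have left it, so on-drug scores may also fall with time. This stands, and it is why the split should supplement the pooled table and not replace it.

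It is also tempting to say that the SAP applies opposite exposure rules to AEs and LSRs. The documents do not go that far: the TEAE window runs from first to last application, so it too includes temporary holds. The difference is that AEs get a separate post-treatment summary and LSRs get no comparable split.

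**Conclusion.** The point holds as a minor gap in a descriptive safety analysis. LSR scores from subjects on and off drug are pooled by visit, and the earlier studies suggest more SB206 than vehicle subjects off drug at Week 12 (about 5-20% vs 1-9%). Understatement of on-drug reactions on SB206, and of the arm difference, is therefore probable at Week 12 and to a lesser extent at Week 8.

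A reader might infer that understatement is certain, or that about a quarter of the arm difference will be lost. The documents support neither. The largest loss, 25 to 18.5 points, needs every cleared subject to stop and every off-drug score to be 0. With AE stops alone it is 25 to about 23 points, and with high off-drug scores there is little change. The 40% and 15% rates are assumptions throughout. No hypothesis test, alpha level or sample size is touched.

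**What to change.** In SAP 13.2, before the Week 12 unblinding:

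- Keep the pooled by-visit tables (14.3.6.1.1 to 14.3.6.1.5) as the all-treated summary.
- Add supplementary rows by treatment status at the visit, with counts per arm: on drug; off drug for clearance; held or stopped for an AE; off drug for another reason. Derive status from the diary and end-of-treatment data. State the window for on drug (for example, at least one application in the 7 days up to the visit) and which category takes precedence when a hold began inside that window.
- Add each subject's worst on-treatment LSR composite and component score. Subjects who stop early still contribute to it, so it does not depend on who stays on drug.

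The cost is SAP wording and extra rows from data already collected. The downside is small: later on-drug rows are selected for tolerability and must be read with the off-drug counts beside them.

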Safety Endpoints	
 • Incidence of treatment-emergent adverse events • Change from Baseline in LSR scores • Change from Baseline in abbreviated physical examinations • Concomitant medications reported • Proportion of subject(s) with reported scar(s)
Other Endpoint	
 • Change from Baseline in BOTE scores
Exploratory Endpoints	
 • Percent change from Baseline in number of treatable MC at Weeks 2, 8, and 12 • Proportion of subjects achieving a lesion count of 0 or 1 of all treatable MC at Weeks 2, 4, and 8 • Proportion of subjects achieving at least a 90% reduction from Baseline in the number of all treatable MC at Weeks 2, 4 and 8 • Proportion of subjects achieving at least a 75% reduction from Baseline in the number of all treatable MC at Weeks 2, 4, 8 and 12 • Absolute change from Baseline in number of treatable MC at Weeks 2, 4, 8 and 12 • Proportion of subjects with complete clearance of all treatable MC at Weeks 2 and 4 • Time to complete clearance of all treatable MC • Proportion of subjects who have a recurrence of MC after the first visit at which complete clearance was observed • Subject-reported spread to household members as measured by any new occurrence of MC in household members of subjects at Weeks 2, 4, 8, 12 • Investigator Global Severity Assessment at Baseline, Week 12 and 24 • Subject Global Severity Assessment at Baseline, Week 12 and 24 • Investigator Global Impression of Change at Week 12 and 24 • Subject Global Impression of Change at Week 12 and 24
Number of Sites	Approximately 55 sites in the United States
Study Duration	
Estimated start date: 01 Sep 2020
 
Projected stop date: 31 Mar 2021
 
Estimated duration: 3.5 months of enrollment

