Subjects who discontinue the study prior to the Week 12 visit will be asked to complete the Week 12 visit assessments in the clinic; this will be recorded as an Early Termination (ET1) visit. Subjects who discontinue from the study after Week 12 but prior to Week 24 will be asked to come to the site to complete Week 24 assessments; this visit will be recorded as an ET2 visit.

Safety assessments include BOTE Inflammation Scores, Local Skin Reaction (LSR) scores, adverse event collection, including scarring/keloid and urine pregnancy tests (UPTs). Safety

assessments will be completed at specified visits through Week 12. Adverse events and concomitant medications will be reviewed and updated as needed at each visit through Week 24.

Inflammatory reactions around MC lesions has been associated with imminent resolution of MC (sometimes referred to as “beginning-of-the-end” [“BOTE”] sign). The investigator (or designated evaluator) will assess the presence and overall degree of inflammatory reactions at MC lesions at Baseline (pre-dose) and Weeks 2-12 using the BOTE Inflammation Score (Section 7.1.2.1). BOTE may be associated with itch, but not pain. BOTE is usually asymptomatic, self-limited, localized to individual MC lesions, and does not require discontinuation of study treatment or additional treatment. LSR is generally more diffuse, associated with significant itch or tenderness, may necessitate discontinuation of study treatment, and may need treatment for symptomatic relief (e.g. a topical corticosteroid or topical anesthetic). For very severe LSRs, systemic corticosteroids may be considered (Section 7.2.3 for additional details). Investigators will assess the treatment area at each scheduled visit and use their medical judgement to differentiate between BOTE and LSRs. BOTE Inflammation Score and LSR component scores will be recorded at each visit. When LSRs are clinically significant at the application site, the investigator should report the condition as AE(s).

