10.2 Population

10.2.1 Sample Size Rationale

Approximately 850 subjects, 6 months of age and older, with a minimum of 3 and a maximum of 70 MC lesions at Baseline will be randomized in a 1:1 (active:vehicle) scheme. The sample size assumptions for this study were informed by the integration of the completed phase 3 studies [NI-MC301](#) and [NI-MC302](#). Multiple replications of simulated random sampling of the integrated NI-MC301 and NI-MC302 data was performed to ensure the sample size assumptions align with the proposed design of NI-MC304. This includes the 1:1 ratio (active:vehicle) and the percentages observed in NI-MC301 and NI-MC302 for each stratum of each of the stratification

factors: investigator type, number of randomized subjects per household, and baseline BOTE score that are planned for NI-MC304.

The analysis of the proportion of subjects with complete response of all treatable MC at Week 12 within the Intent-to-Treat (ITT) Population of the multiple replications of simulated random sampled integrated data yields rates of 20% for vehicle and 29.5% for SB206 10.3% QD with the covariate-adjusted treatment difference was 9.5%. A sample size of 850 subjects (425 subjects in the SB206 10.3% QD group and 425 subjects in the vehicle group) will provide 90% power for a 2-sided alpha test of size 0.05 to detect an absolute difference of 9.5% when the vehicle response rate is 20%.

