## 12. OTHER ANALYSES

The following analyses of BOTE vs lesion count will be presented:

- Percent change from Baseline in the number of treatable MC at each visit in relation to the Baseline BOTE score comparing No Inflammation vs Inflammation within each treatment group through a repeated measures mixed model with number of randomly assigned subjects in household (1 subject vs 2 subjects), investigator type (dermatologist

vs other), BOTE score at Baseline (no inflammation [BOTE=0] vs mild/moderate/severe/very severe inflammation [BOTE $\geq$ 1]), BOTE score at Baseline by visit interaction, age, and baseline lesion count as covariates with a compound symmetry covariance matrix.

- Percent change from Baseline in the number of treatable MC at Week 12 in relation to the highest post-baseline BOTE score during treatment will be summarized descriptively.
- Percent change from Baseline in the number of treatable MC at Week 12 in relation to the highest BOTE score at any visit (including Baseline) will be summarized descriptively.
- Percent change from Baseline in the number of treatable MC at each visit in relation to the BOTE score at Week 2 will be summarized descriptively.

In these analyses, the BOTE scores will be analyzed in the ITT Population as follows:

1. Dichotomized:
  - a. Score of 0: No Inflammation
  - b. Score of 1, 2, 3, or 4: Mild to Very Severe

A shift table comparing the baseline BOTE score to each scheduled post-baseline assessment will be presented for the ITT Population.

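### BOTE is scored even after clearance, so the planned shift table cannot separate subjects with no lesions left from subjects whose lesions persist without inflammation

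*Protocol*

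**What the plan says.** Protocol section 4.1 has the investigator assess the "presence and overall degree of inflammatory reactions at MC lesions", and describes BOTE as a sign that lesions are about to resolve. Section 5.2 requires 3 to 70 treatable lesions at Baseline, so every eligible subject starts with lesions to score.

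After Baseline this no longer holds. The schedule footnote in Protocol section 1.2 allows scoring "regardless of whether lesions are present and whether study drug is applied". Section 6.6 asks for the score at each scheduled visit "even if the subject is not going to be dosed or if the MC lesions have cleared". Protocol Table 5 runs from 0 to 4. Score 0 means that no local inflammation is seen, and there is no level for a subject without lesions.

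The named endpoint is "Change from Baseline in BOTE scores" (Protocol section 1), and section 3 gives it the objective of comparing SB206 with vehicle. Its output in SAP section 12 is: "A shift table comparing the baseline BOTE score to each scheduled post-baseline assessment will be presented for the ITT Population". Protocol section 10.3.5 plans the same table for the Safety Population, while SAP section 14 reports no change from the protocol. SAP section 6 sets by-visit denominators as all subjects with data at the visit, so scored subjects who have cleared are included.

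**The concern.** A post-baseline 0 can mean two opposite things: the lesions are gone, or they persist with no sign of resolving. For a sign that is supposed to precede clearance, these should not share a cell. The proportion of zeros that come from cleared subjects also depends on the clearance rate, which is the primary endpoint. A difference between arms in the table therefore mixes two components: how many subjects still have lesions, and how often the remaining lesions are inflamed. Only the second speaks to the BOTE objective. The planned table gives no means of separating them.

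**Working it through.** **Inputs from the documents**
- Planning rates (Protocol section 10.2.1): the simulated sampling "yields rates of 20% for vehicle and 29.5% for SB206 10.3% QD".
- Sample size: 425 per arm.
- Week 8 clearance in the earlier phase 3 studies (Protocol section 2.1.4.3): 15.3% vs 10.3% in NI-MC301, 13.9% vs 5.9% in NI-MC302.
- Study discontinuation in those studies (Protocol section 2.1): 15.3% and 17.2%.

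**Assumed, because the documents give no figure**
- q, the share with BOTE of 1 or more among subjects with lesions: 10% to 50%.
- r, the same share among cleared subjects: 0 to 40%.

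**1. The plan's own figure.** Protocol section 10.2.1 claims 90% power, two-sided at 0.05, for these two rates. With a pooled rate of 0.2475:
- null standard error = √(2 × 0.2475 × 0.7525 / 425) = 0.02961
- alternative standard error = √(0.20 × 0.80 / 425 + 0.295 × 0.705 / 425) = 0.02943
- z = (0.095 − 1.96 × 0.02961) / 0.02943 = 1.26, which is power of 89.6%

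The stated 90% is reproduced, so the clearance rates are taken as given. The documents state no figure for BOTE.

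**2. Displayed share.** With clearance c, the inflamed share among all scored subjects is (1 − c)q + c·r. With q and r equal in both arms, the difference between arms is (c_SB206 − c_vehicle)(r − q).

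**3. Week 12, r = 0.** The ratio is 0.705 / 0.80 = 0.881 for any q.

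| q | SB206 | Vehicle | Difference (points) |
|---|---|---|---|
| 10% | 7.05% | 8.00% | −0.95 |
| 30% | 21.15% | 24.00% | −2.85 |
| 40% | 28.20% | 32.00% | −3.80 |
| 50% | 35.25% | 40.00% | −4.75 |

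For scale, the standard error of the difference at q = 30%, ignoring household clustering, is √(0.2115 × 0.7885 / 425 + 0.24 × 0.76 / 425) = 2.9 points. The gap there is about one standard error.

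**4. Clearance among observed subjects.** The planning rates count missing subjects as not cleared, but the table omits them. Dividing both rates by 1 − 0.153 or 1 − 0.172 (equal dropout in both arms assumed) gives ratios of 0.853 or 0.849, and a difference of −3.4 points at q = 30%.

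**5. Week 8, r = 0.** The ratios are 0.847 / 0.897 = 0.944 (NI-MC301) and 0.861 / 0.941 = 0.915 (NI-MC302). At q = 30% that is −1.5 and −2.4 points.

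**6. If cleared skin can be scored as inflamed.** At Week 12 and q = 30% the difference is 9.5 × (r − 0.30) points: −1.90 at r = 10%, 0 at r = 30%, and +0.95 at r = 40%.

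**7. If SB206 erythema is scored as BOTE.** With r = 0, the gap is cancelled when SB206 raises the inflamed share among subjects with lesions by (0.80 / 0.705 − 1)q. That is 1.3 points at q = 10%, 4.0 at 30% and 6.7 at 50%. Summing severities in Protocol Tables 3 and 4, application site erythema was 29/235 (12.3%) vs 3/116 (2.6%) and 26/237 (11.0%) vs 0/117, gaps of 9.8 and 11.0 points. These are adverse event rates accumulated over follow-up, not BOTE scores at a visit, so they show only that an offset of this size is possible.

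**8. What splitting the table does.** At q = 40% and r = 0, with all scored subjects as denominator, the cells for lesions present and inflamed still total 28.2% vs 32.0%. The count-0 part now shows 29.5% vs 20% beside them, so the cause is visible. Among subjects with lesions, 28.2 / 70.5 and 32.0 / 80.0 are both 40%. Discarding scores at count 0 could widen the gap: with q = 40% and r = 10%, keeping all scores gives 31.15% vs 34.0% (2.85 points), and discarding gives 28.2% vs 32.0% (3.8 points).

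**The case against.** The strongest reply is that BOTE is also listed as a safety assessment (Protocol section 4.1), and that investigators examine the treatment area rather than individual lesions. As a description of treated skin, 0 on clear skin is a correct value, and a higher score on skin that has just cleared is a real observation. This stands, and it is why no recorded score should be dropped.

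Other outputs also cover part of the ground. SAP section 13.3 counts subjects with at least one moderate post-baseline BOTE score, which later clearance does not erase. SAP section 12 relates change in lesion count to the Baseline, Week 2 and highest BOTE scores. These bear on whether BOTE predicts clearance. None of them splits a visit's BOTE scores by whether any treatable lesion was present at that visit. The Week 2 analysis sets score and count of the same visit together only at Week 2, and then as mean-type summaries of percent change.

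A reader might infer that the table will show less inflammation on SB206 than on vehicle. The documents do not support that. Neither document says that a cleared subject scores 0, no inflamed share is given, and steps 6 and 7 show that the gap can vanish or change sign. Nor does the point reach the efficacy conclusions: BOTE is an other endpoint outside the fixed sequence in SAP section 10.7, and no between-arm test of BOTE is planned.

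**Conclusion.** The point holds as a defect of presentation. The lesion-based definition and the scoring rule diverge once a subject clears, and no planned output repairs this, so the shift table cannot answer the BOTE objective on its own.

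Under two assumptions (cleared subjects mostly score 0, and inflammation where lesions remain is equal in both arms), the effect at Week 12 is a ratio of 0.88, or about 0.85 among observed subjects, and roughly 1 to 5 points at the planning rates. It is smaller at Week 8. The net direction in the actual data cannot be known beforehand. The change is worth making because it is nearly free, not because a trial conclusion is at risk.

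**What to change.** In SAP section 12 and Protocol section 10.3.5:

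- Split each post-baseline visit of Table 14.2.3.12.5 by the treatable lesion count of the same visit (0, or at least 1). Within each part show the recorded BOTE scores 0 to 4 by arm.
- Keep the scores recorded at count 0, and add a line for any subject with a score but no count.
- Give percentages of all scored subjects. As a supplement, give percentages among subjects with lesions at the visit, labelled as a subset defined after randomisation and so not a randomised comparison.
- At Week 4, footnote that a count of 0 from a remote visit is not confirmed clearance, since Protocol section 7.1.1 accepts only an in-clinic count for that.
- Reconcile the population of the table: Safety in Protocol section 10.3.5, ITT in SAP section 12. Record the outcome in SAP section 14.

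The cost is a larger descriptive table with some small cells. Lesion count and BOTE are both already scheduled at Weeks 2, 4, 8 and 12, so no new data are needed.
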